9.2 Study Procedure

To be eligible for screening, subjects must have a documented positive SARS-CoV-2 test result within 5 days of first dose of study drug and have at least one ongoing symptom consistent with SARS-CoV-2 infection rated as at least mild to moderate in the opinion of the investigator. The subject's earliest symptom must have an onset date within 5 days of first dose of study drug.

Subjects will undergo screening (day -4 to 0) for confirming eligibility for participation in the study. Study Day 1 includes randomization visit.

Subjects will be randomized to a cohort as described above.

Screening activities as well as randomization can take place on the same day as a combined Screening/Day 1 visit, if the site team is able to obtain Screening lab results on the same day. Otherwise, Day 1 is to take place as soon as Screening lab results are available.

Study Day 1 and first dose of study drug must take place ≤ 5 days from onset of first symptom.

Subjects may be hospitalized as many as 9 days in the study (day 0 to 8) or more for the PK sample as per Investigator discretion.

For subjects participating in the PK subset,

Protocol for clinical study of Brequinar

Protocol No.: 21-VIN-0372

Version No.: 2.1; Dated: 29 Dec 2021

Supersedes: 02; Date of Supersedes: 30 Sep 2021

Blood samples for estimating brequinar concentrations will be drawn (PK):

- Day 1: Pre-dose (within 1 hour prior to study drug administration) and post dose at 1h, 2h, 4h, and 8h; note that the 8h sample is to be obtained prior to the next dose of dipyridamole;
- Days 2 – 5 pre-dose and Day 8.

Aliquots of the NP/OP swab samples are to be stored at the testing laboratory for possible additional virological testing.

Screening visit and study visits on Days 1, 8, 15, 22 and 29 will be either in person or a combination of in-person and virtual visit (telemedicine or other remote technique) or by visit to patient's home by site team.

Study visits on Day 4 and 12 may be virtual visits (telemedicine or other remote technique) or in person.

On Days 2, 3, 5, 6 and 7, the site will have a telephone call / or in-person communication with the subject for changes in concomitant medications and assessment of adverse events (same will also be captured by the subject using a patient diary card or these visits will be conducted in person).

Note:

- Study procedures are presented in detail in the Schedule of Events.
- Days 1, 8, 15 and 29 require sample collection for performing laboratory tests and will be conducted at the site or via home visit.
- Any in-person visit may also have telemedicine or telephone components if all study activities cannot be completed in person.
- The visits that include bloodwork must be conducted at the study site or arrangements made for sample collection at the subject's home or other appropriate location.
- Site staff (in case of an in-person visit) or subjects (in case of a remote visit) will assess respiratory rate, heart rate, body temperature and SpO₂ (a thermometer and pulse oximeter are to be provided to subjects who are home quarantined, leave the hospital or are unable to return for study visits).
- Subjects will record details of concomitant medications, adverse events in the patient diary card (PDC).
- Subjects will complete a symptom assessment form on designated days daily during the study period (days 1 – 8, 12, 15, 22, and 29).
- In case the subject is hospitalized during the course of study, the activities specified in scheduled visits / time points will be carried out within the hospital facility.
- Study completion or the reason for study discontinuation will be recorded in the source document and the eCRF.

DSMB Meeting:

A Data Safety Monitoring Board (DSMB) will meet to review the safety and scientific conduct of the study. At a minimum, the DSMB will review the protocol and study design prior to study start, after the end of the first part of the study prior to the expansion phase, and at the end of the study.

Protocol for clinical study of Brequinar

Protocol No.: 21-VIN-0372

Version No.: 2.1; Dated: 29 Dec 2021

Supersedes: 02; Date of Supersedes: 30 Sep 2021

At each interim meeting the DSMB members will determine whether to stop the study, amend the protocol, or continue the study per protocol. The study enrollment will not be suspended for routine DSMB meetings.

The DSMB will be convened and enrollment suspended if Cohort-Level Stopping Criteria are met. The DSMB may allow the enrollment to resume following their review if safety criteria are met.

9.3 Hospitalization

Subjects may be hospitalized for approximately 9 days (day 0 to 8) in the study as per Investigator discretion for the PK blood sample draws. Subjects may leave after this period (if medically discharged) after the Day 8 blood work has been drawn. Extended stays beyond study Day 8 are permitted if the facility is a dedicated COVID-19 unit or other relevant hospital type or if per the Investigator the extended stay facilitates study procedures; this continuation will not be considered as an SAE. However, prolongation of hospitalization due to increase in disease severity or any other safety concerns related to the subjects will be considered as an SAE.

Hospitalization for the purpose of PK sample collection may be done at Investigator's discretion, in this case hospitalization may be for selected few days and may not be for entire 8 days duration. Appropriate documentation of the same will be done in source file.

9.4 Unscheduled Visits and Early Discontinuation Visit

An Unscheduled Visit is allowed at any time, for any reason, if in the Investigator's opinion it is warranted. If the Unscheduled Visit is due to an AE, the Investigator will determine whether additional visits are needed.

If a subject is discontinued from the study during an Unscheduled Visit, the Unscheduled Visit will be referred to as an Early Discontinuation Visit and all procedures scheduled for End of Study visit will be performed.

If the Unscheduled Visit is not an Early Discontinuation Visit (i.e., the subject will continue to take part in the study), then the reason for unscheduled visit is documented and required procedures at the discretion of investigator considering the reason for visit will be performed.

If the Investigator determines that the subject's condition has worsened to the degree that it is unsafe for the subject to continue in the study, the subject may be discontinued from the study as treatment failure and a standard of care treatment may be advised at the Investigator's discretion.

In case of ongoing AEs, telephonic safety follow up will be continued until resolution or stabilization of AEs or up to 30 days after administration of last dose of IMP, whichever is earlier.

9.5 Sample Collection Procedure

Blood collection for PK analysis:

PK blood samples will be collected through an indwelling intravenous cannula (Venflon or similar) placed in the forearm vein of the subjects for up to 24 hours or may also be collected through a fresh vein puncture at each time point. A 10 mL of blood per sample will be obtained using syringe/adaptor and transferred in to pre-Confidential

Protocol for clinical study of Brequinar

Protocol No.: 21-VIN-0372

Version No.: 2.1; Dated: 29 Dec 2021

Supersedes: 02; Date of Supersedes: 30 Sep 2021

labelled vacutainers containing K₂EDTA as anticoagulant. Filled vacutainers will be placed on wet ice bath (below 10 °C) during sample collection activity and until storage of plasma.

Time of collection of each blood sample (as displayed in the calibrated digital clock) will be recorded in 24-hour clock format (hh:mm) on the PK blood sample collection log and same will be transcribed to eCRFs.

If an intravenous indwelling cannula is placed, maintain this as long as possible by injecting 0.5 mL of 5 IU/mL of heparin in normal saline solution or per hospital's usual practice to maintain the cannula patency. When sampling through the cannula, collect study blood samples after discarding the first 0.5 mL of heparinised blood from the cannula. If insertion of cannula is not possible, alternatively blood samples may be drawn by a fresh venipuncture or in case of blockade in an existing cannula, extra heparinised saline will be injected to stimulate the cannula and later blood samples will be collected after discarding the heparinised blood or central line. If the time window does not allow, it is recommended to directly use a disposable syringe for extraction, and appropriately dispose of the retained needle after blood collection.

The blood samples will be withdrawn using syringe or adaptor and transferred into pre-chilled (maintained at temperature below 10 °C), pre-labelled (mentioning Site number, Protocol number, Subject number, Period number, Sampling time point and Sample ID) sample collection tubes containing K₂EDTA as an anticoagulant kept on wet ice bath (below 10 °C) until centrifugation. Immediately following blood collection, the vacutainers are to be gently inverted 5 - 7 times to mix the anticoagulant.

It is recommended that collected blood samples be placed on wet ice bath (below 10 °C) from the point of collection until storage of plasma.

NP/OP Sample Collection for qPCR

The Laboratory Manual will provide details regarding collection, processing, storage and shipment for qPCR samples.

9.6 Sample Size

No statistical powering has been performed for this study. The number of subjects is designed to provide information on the safety, tolerability, and efficacy of the IMP tested in this study. In Part 1, approximately 64 subjects will be randomized to up to 4 cohorts of 5 consecutive days of one of the following regimens in addition to SOC in 2:1:1 ratio as shown below:

Treatment Arm ^a	Day 1	Day 2	Day 3	Day 4	Day 5
Brequinar + Dipyridamole (N=8)	BRQ XX mg OD DPY 75 mg TID				
Brequinar (N=4)	BRQ XX mg OD				
Placebo (N=4)	PBO XX mg OD				

Protocol for clinical study of Brequinar

Protocol No.: 21-VIN-0372

Version No.: 2.1; Dated: 29 Dec 2021

Supersedes: 02; Date of Supersedes: 30 Sep 2021

^aAll subjects will also received standard of care (SOC).

The brequinar dose will start at 50 mg and may be escalated to 100 mg, 150 mg, and 200 mg if safety criteria are met for each cohort (see Safety Criteria below).

The hospital pharmacist is to be unblinded. Bulk supplies of investigational medicinal product (IMP) of brequinar 50 mg, brequinar 100 mg, dipyridamole 75 mg, brequinar placebo 50 mg and brequinar placebo 100 mg will be supplied to the unblinded hospital pharmacist.

The unblinded hospital pharmacist is to prepare the assigned IMP for each individual subject at that institution and create an appropriately labeled bottle/zip lock bag of study medication sufficient for a 5-day treatment course. The randomization assignment will be provided via an IWRS.

Alternatively, the hospital pharmacist and study team may decide to distribute IMP on a daily basis for 5 days for brequinar and dipyridamole while the subject is hospitalized, depending on the most convenient method.

9.7 Patient identification and Randomisation

Randomization will be carried out using SAS® (SAS Institute Inc., USA) version 9.4 or higher. Randomization will be done in blocks using PROC PLAN such that the design is unstructured. The treatment allocation will be determined according to the randomization schedule and randomization schedule will be done per cohort.

Screening and Randomization Numbering

Each subject will be assigned a unique number that will serve to identify laboratory specimens and all documents, and if randomized throughout the study. If a subject fails to qualify for allocation to the study i.e. is a screen failure, the subject's unique number will not be used for another subject.

Screening number will be a combination of center number, project number and subject number. The center number will be assigned by Veeda to the investigative site (e.g. A, B, C, D) and subsequent sites are assigned consecutive alphabet numbers. Upon signing the informed consent form, the subject will be assigned a screening number by the Investigator. At each site the first subject consented is assigned screening number e.g. A-21-0372-001, and subsequent subjects are assigned consecutive numbers (e.g., the second subject consented is assigned screening number A-21-0372-002, the third subject is assigned screening number A-21-0372-003). Once a screening number is assigned to a subject, that number will not be reused.

If the subject is deemed eligible for enrollment into the study and will commence dosing, then a randomization number will be assigned via IWRS as defined in the randomization plan. Subjects will be randomized with the next qualifying subject given the next available randomization number.

A source document maintained at the site will link the screening number to the randomization assignment number (once assigned) and the same will be reflected in screening and enrollment log of Investigator site file.

The assigned subject number will be recorded in the CRF of the subject.

Protocol for clinical study of Brequinar

Protocol No.: 21-VIN-0372

Version No.: 2.1; Dated: 29 Dec 2021

Supersedes: 02; Date of Supersedes: 30 Sep 2021

The personnel involved in dispensing of study drug and verification of dispensed study drugs will be accountable for ensuring compliance to randomization schedule.

9.8 Blinding

Instructions provided in this section are a general description of operational procedures. Investigators are instructed to always refer to latest version of respective study plans/manuals for detailed and latest information.

The intent of blinding is to limit the occurrence of conscious and unconscious bias in the conduct and interpretation of the clinical study. The essential aim of blinding, therefore, is to prevent identification of the treatments by the Investigator and others associated with the conduct of the study until all such opportunities for bias have passed.

Due to unavailability of a matching dipyridamole placebo, subjects in the brequinar-dipyridamole treatment arm will have a daily dose of one brequinar capsule of appropriate strength and three 75 mg dipyridamole tablets whereas subjects in the SOC + brequinar only arm will receive only brequinar capsule(s) daily at the appropriate strength. Subjects in the SOC + brequinar placebo arm will receive only brequinar placebo capsule(s) daily at the appropriate strength. No dipyridamole placebo tablets will be provided to the subjects assigned to the brequinar only or brequinar placebo treatment arms.

The Sponsor will provide investigational medicinal product (IMP) bulk drug supplies to the ThermoFisher depot. ThermoFisher will supply each site with bulk supplies of brequinar 50 mg and 100 mg capsules (50 count bottles) and dipyridamole (100 count bottles). An unblinded independent site staff member (e.g., hospital pharmacist) will dispense the IMP for each subject according to the assigned cohort and randomization schedule, and perform IMP accountability by collecting used and unused products. The unblinded pharmacist will not participate in the clinical trial assessments in order to minimize potential bias, and will be instructed not to discuss the IMP with assessors and other blinded study personnel.

The unblinded pharmacist should use an opaque bottle or envelope to ensure that the blinded study team is not able to see the IMP. The subjects will be instructed not to reveal the contents of the bottle(s)/envelope(s) to the blinded investigator or study staff.

The blinded investigational staff performing the assessments and data analysts (with the exception of the biostatistician who will undertake the generation of the randomisation scheme) will remain blinded to the identity of the treatment assignments for individual subjects from the time of randomization until database lock, using the following methods:

- Randomization data will be kept strictly confidential until the time of unblinding, and will not be accessible by anyone else involved in the study.
- Only the unblinded pharmacist or designate will be involved in dispensing, administering and collecting the study medication.
- Unblinding of blinded study personnel will be permitted only in the case of patient in emergency condition and at the conclusion of the study.

Protocol for clinical study of Brequinar

Protocol No.: 21-VIN-0372

Version No.: 2.1; Dated: 29 Dec 2021

Supersedes: 02; Date of Supersedes: 30 Sep 2021

Data that may potentially unblind the intervention assignment (i.e., study intervention preparation/accountability data, intervention allocation or other specific laboratory data) will be handled with special care to ensure that the integrity of the blinding is maintained and the potential for bias is minimized.

Site specific randomization schedule, drug dispensing logs, drug accountability forms and other papers identifying treatment allocation are kept in a separate binder in a locked cupboard to which the investigators does not have access. Trial staff is provided training in the importance of maintaining blinding, and trial medication delegates/trial coordinators are also helped to set up systems at the clinic.

Every effort must be made to limit the number of unblinded study personnel to ensure the integrity of this study.

In the event of a Quality Assurance audit after the study has been unblinded, the auditor(s) will be allowed access to unblinded study intervention records at the site(s) to verify that randomization/dispensing has been done accurately.

9.8.1 Unblinding of treatment assignment

If necessary, the Investigator may be required to unblind a participant if an adverse event (AE) meets criteria in order to fulfill expedited regulatory reporting requirements. In this event, Investigator will inform the same to sponsor or its designee/study medical monitor if possible to discuss the particular situation, before breaking the blinding unless this could delay emergency treatment of the participant. Telephone contact with the medical monitor will be available 24 hours per day, 7 days per week. The Sponsor/CRO PV and/or safety review team will access the AE report and conclude whether unblinding is required. Once Sponsor/CRO PV and/or safety review team conclude that study participant requires the unblinding, Investigator will ask unblinded study personnel to provide the treatment sequence.

Investigators are instructed to always refer to latest version of respective unblinding procedure manuals for detailed and latest information.

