7.0 STUDY ENDPOINTS

Primary Endpoints:

- Frequencies of grade 3 and 4 toxicities and serious adverse events (SAEs) considered by the investigator to be related to the combination, brequinar alone or placebo alone.

Secondary Endpoints:

- qPCR SARS-CoV-2 levels through Day 29 and at days 4, 8, 12, 15, 22, and 29;
- Time to symptom improvement through Day 29;
- Percentage of subjects requiring hospital admission/re-admission as an in-patient for >24 hours through Day 29;
- Percentage of subjects requiring medical attended visits, e.g., hospitalization, emergency room visits, Urgent Care/Family Doctor visits through Day 29;
- Percentage of subjects requiring supplemental support such as oxygen through Day 29.

Exploratory Endpoints (PK):

- Analysis of brequinar's pharmacokinetic profile in a subset of patients that have received brequinar as a part of therapy and have consented to provide PK samples.

Clinical improvement will be defined as a 2-point or greater improvement on an 8-point WHO ordinal scale in every subject measured on each designated day, from the date of randomization through day 29. This scale has been used in the current COVID-19 outbreak.

Ordinal Scale for Clinical Improvement

Patient State	Descriptor	Score
Uninfected	No clinical or virological evidence of infection	0
Ambulatory	No limitation of activities	1
	Limitation of activities	2
Hospitalized	Hospitalized, no oxygen therapy	3

Protocol for clinical study of Brequinar

Protocol No.: 21-VIN-0372

Version No.: 2.1; Dated: 29 Dec 2021

Supersedes: 02; Date of Supersedes: 30 Sep 2021

Mild disease	Oxygen by mask or nasal prongs	4
Hospitalized	Non-invasive ventilation or high-flow oxygen	5
Severe Disease	Intubation and mechanical ventilation	6
	Ventilation + additional organ support – pressors, RRT, ECMO	7
Dead	Death	8

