All AEs (serious or not) will be followed to resolution (the subject's health has returned to his/her baseline status or all variables have returned to normal or clinically acceptable level), an outcome is reached, stabilization (the Investigator does not expect any further improvement or worsening of the event), or the event is otherwise explained regardless of whether the subject is still participating in the study. Where appropriate, medical tests and examinations will be performed to document resolution of event(s).

The Investigator should institute any supplemental investigations of SAE based on their clinical judgment of likely causative factors.

If required, a follow-up report including all relevant new or reassessed information (e.g., concomitant treatment, medical history) obtained on the SAE will be prepared and same will be marked "Follow-up report". Follow up reports are to be sequentially numbered to allow tracking. These reports will be sent to the sponsor/CRO.

Adverse events occurring between informed consent and the last visit

The investigator should follow up on all AEs which occurred from signature of study-specific informed consent until the last visit of the subject, at which point the outcome assessment is documented in the CRF.

Ongoing serious adverse events at the time of last visit

For any SAEs still ongoing at the time of last visit considered to be related to IMP, the investigator should continue to follow-up until the SAE has resolved or has stabilized / is judged permanent for SAEs, and for up to 30 days after the last visit of subject for non-related SAEs. Where appropriate, medical tests and examinations will be performed to document resolution of event(s). The investigator should send SAE follow-up reports including all relevant new or reassessed information (e.g., concomitant treatment, medical history) obtained on the SAE /pregnancy to the sponsor/CRO.

If a subject dies during participation in the study and an autopsy is performed, a copy of the report must be submitted.

Serious adverse events occurring after the last visit

Any SAEs experienced after the last visit should only be reported to sponsor if the investigator suspects a causal relationship to study treatment. The investigator must report the SADR to recipients as per the 'SAE Reporting' section 12.10.

Protocol for clinical study of Brequinar
 Protocol No.: 21-VIN-0372
 Version No.: 2.1; Dated: 29 Dec 2021
 Supersedes: 02; Date of Supersedes: 30 Sep 2021

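### Section 9.8.1 passes the treatment code for expedited reporting to the blinded investigator, a route that 9.8 does not allow, and nothing fixes the causality call before the code is given

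*Combined protocol and SAP*

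**What the plan says.** All references are to protocol Version 2.1. Version 01 has the same blinding wording.

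- **Section 9.8** names the investigator among those to be kept from identifying treatments. It says that assessors and data analysts "will remain blinded to the identity of the treatment assignments for individual subjects from the time of randomization until database lock". It allows two exceptions: "Unblinding of blinded study personnel will be permitted only in the case of patient in emergency condition and at the conclusion of the study".
- **Section 9.8.1** adds another: "the Investigator may be required to unblind a participant if an adverse event (AE) meets criteria in order to fulfill expedited regulatory reporting requirements". The decision lies elsewhere: "The Sponsor/CRO PV and/or safety review team will access the AE report and conclude whether unblinding is required". Once they decide that it is, "Investigator will ask unblinded study personnel to provide the treatment sequence".
- **Section 9.8.2** deals separately with emergency code breaks.
- **Section 7.0**, repeated in 15.4, defines the primary endpoint as frequencies of Grade 3 and 4 toxicities and SAEs "considered by the investigator to be related to the combination, brequinar alone or placebo alone".
- **Section 12.9** has an unblinded CRO physician apply the declared-safe criteria, but takes relatedness from the investigator.
- **Section 12.11**, on SAEs still ongoing at the last visit, says: "The investigator should send SAE follow-up reports including all relevant new or reassessed information". The examples it gives are concomitant treatment and medical history.

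**The concern.** A site cannot follow both 9.8 and 9.8.1. If it follows 9.8.1, the code reaches the person whose judgment the blind is meant to protect.

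Three features of the design make that judgment sensitive to knowledge of the arm.

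1. Section 12.13 counts a possible relationship as related and an unlikely one as not related. An event can be possible even when the disease or other drugs could explain it. In symptomatic COVID-19 that boundary is soft.
2. The endpoint counts events attributed to placebo. That frequency is a useful comparator only if the call was made without knowing that the subject was on placebo.
3. There is no dipyridamole placebo, so subjects can tell whether they are taking tablets. The assessor's blind is the main protection left.

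At stake are the between-arm frequencies of the primary endpoint and an input to the cohort safety decision.

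**Working it through.** **1. Is 9.8.1 merely the emergency exception restated?** No. Emergencies have their own section, 9.8.2. The trigger in 9.8.1 is an expedited-reporting requirement, with no emergency needed. It is a third route that 9.8 excludes.

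**2. Who receives the code?** Pharmacovigilance or the safety review team decides; the investigator requests and receives it. Section 10.1 lists the investigator as a blinded assessor.

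**3. Which endpoint events can take this route?** Section 9.8.1 does not define the qualifying criteria. The clearest overlap is SAEs thought to be related. Section 12.12 includes in Grade 3 events for which hospitalisation or its prolongation is indicated, and 12.10 makes both of these grounds for an SAE, so a good part of Grade 3/4 is also serious. Non-serious Grade 3 laboratory events, and lower grades counted by the any-grade criterion, need not trigger it.

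**4. Is causality fixed first?** The sequence in 9.8.1 is AE report, decision, code. Section 12.9 requires association with study medication to be recorded for every AE, so a first call probably precedes the code. No section says that it must, locks it, or states which call counts if it changes.

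**5. Weight of one event.** Part 1 reproduces: 4 × (8 + 4 + 4) = 64. One event is 1/4 = 25 percentage points in a brequinar-alone or placebo arm of a cohort, and 1/8 = 12.5 points in the combination arm. If arms are pooled over four cohorts (my assumption), one event is 1/16 = 6.25 points for placebo or brequinar alone and 1/32 = 3.1 points for the combination.

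**6. How often could one call matter to the safety criteria?** They allow no related Grade 3 or higher toxicity and at most one related SAE. There are 8 + 4 = 12 subjects on active drug per cohort. The chance of at least one Grade 3 or higher AE among them is 1 − (1 − p)^12, with p assumed:

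| p | P(at least one) |
|---|---|
| 1/56 = 1.8% (earlier outpatient study, brequinar group) | 19% |
| 5% | 46% |
| 10% | 72% |

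If a share r of such events is called related, the chance of none is (1 − pr)^12. Moving r from 0.25 to 0.75 changes it from 95% to 85% at p = 1/56, from 86% to 63% at 5%, and from 74% to 39% at 10%. Both values of r are assumed and are applied to every Grade 3 or higher event, whether or not it would be unblinded. These figures show how much rests on the relatedness call; they do not estimate the bias caused by 9.8.1.

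**The case against.** The strongest reply is that this is a wording mismatch with little consequence. Section 9.8.1 is conditional, and its order suggests that a causality call exists before the code is requested. Section 9.8 describes itself as general and, like 9.8.1, refers to manuals that are not among the documents; these may restrict disclosure or fix the timing. The primary endpoint is not formally tested and the study is not powered, so no error rate is affected. Some stopping rules ignore relatedness: the Grade 4 individual criterion, and the cohort rule of five or more subjects with Grade 3 or higher AEs.

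All of this stands as a limit on size. It does not remove the contradiction, and the protocol text itself still sends the code to the assessor without a lock.

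A reader might infer from 12.11 that the protocol expects causality to be revised after unblinding. It does not say so: its examples of new or reassessed information do not include causality. It leaves revision open, no more.

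A reader might also infer that the route pushes escalation in an unsafe direction. The documents do not support that. The criteria concern events related to either study drug. Calling a placebo subject's event unrelated removes one that neither drug could have caused, and calling a combination subject's event related makes the criteria harder to meet.

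**Conclusion.** The contradiction between 9.8 and 9.8.1 is certain. As written, 9.8.1 can tell the assessor the arm for some primary-endpoint events, mainly serious ones thought to be related, with no stated safeguard on the causality call. Bias in the related-event frequencies is therefore possible, not certain. One changed call is worth 12.5 or 25 percentage points within a cohort arm. How often such code breaks would happen is unknown, and the unseen manuals may narrow the gap.

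Two stronger readings go too far. A reader might infer that the investigator is unblinded for precisely the events that make up the endpoint; the qualifying criteria are undefined, and many endpoint events may be non-serious. A reader might also infer that one code break reveals the likely arm of other subjects in the same block; no block size is given, and nothing shows that investigators know which subjects share a block.

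**What to change.** - **Reconcile 9.8 and 9.8.1.** A code break for expedited reporting should be made by, and disclosed only to, sponsor/CRO pharmacovigilance or other already unblinded CRO staff. The investigator and blinded site staff should not receive the assignment.
- **Time-stamp causality.** Require the investigator's causality to be recorded and time-stamped before any such break.
- **Amend 15.4.** State that the primary endpoint summary uses the last causality recorded before unblinding, with later changes listed separately and visible to the unblinded CRO physician.
- **Leave unchanged** the emergency route in 9.8.2 and the safety and escalation criteria in 12.9.

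The cost is wording in 9.8, 9.8.1 and 15.4 and one time-stamp check in the eCRF. An IWRS and an unblinded CRO physician already exist, but no section gives that physician or pharmacovigilance code-break access, so this would have to be set up and stated. Nothing in 12.11 says that the investigator's own report needs the arm. The downside is small: a causality revision made after a code break on genuinely new information appears in the listing and not in the primary summary.
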